### C. Sample size, statistical methods, and power calculation

1. 45 eligible smokers with COPD will be stratified by EC use history (naïve vs. current use) and randomized (1:1:1) to receive brief advice to switch to ECs, single session EC training, or enhanced EC training. Randomization will be determined by computer-generated random numbers. After baseline data collection has been completed, the research assistant will select the sequential study ID number to determine the randomization assignment.
2. This is an open-label trial. There is no blinding involved.
3. Based upon preliminary data, the standard of change in puff duration over two weeks was 1.5 seconds per puff. Assuming a common standard deviation across groups, 15 participants will allow us to obtain a 95% CI with a margin of error of 0.76 for the mean change for brief advice. In the acute phase (i.e., human lab visits 1 and 2), the single episode and enhanced EC training arms will have the same amount of intervention and will be combined. Thus, 30 participants will allow us to obtain a 95% CI with a margin of error of 0.54 for the mean change in puff duration in the combined intervention groups. We also wish to estimate the proportion of subjects who are predominant or complete switchers at Week 12. Fifteen participants in each group will allow us to estimate the 95% CI for the proportion of switchers in each group with a margin of error no greater than 0.25. This data will allow us to determine the sample size needed for a fully powered randomized trial. For the purposes of the current study, we will need 15 complete cases for each group. Due to potential attrition, we will recruit up to 22 participants per group. We will discontinue recruitment when we have 15 complete cases per group.

**D. Subject Criteria (See Vulnerable Populations appendix, if applicable):** Participants will be adult smokers  $\geq 21$  years old and diagnosed with COPD. The study will be open to both men and women. We have chosen to focus on participants with COPD who are unable to quit smoking using pharmacotherapy because their unique smoking profile places them at a high-risk population of smokers that is understudied and stands to experience marked improvements in health and quality of life from quitting smoking. Women who are pregnant, plan to become pregnant, or are breastfeeding will be excluded from the study because tobacco products will be provided, and smoking is associated with low birth weight and premature labor. Children and those  $< 21$  years old will be excluded because the minimum age for purchasing tobacco products is 21 years old.

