## II. Research Plan and Design

**A. Study Objectives:** The overall objective of this application is to evaluate the impact of EC training on changes in puff patterns, nicotine craving and exposure, cigarette smoking, and improvements in COPD-related health effects among smokers with COPD who are unable to quit smoking using pharmacotherapy.

**B. Study Type and Design:** The proposed study is an open label randomized clinical trial of EC training and training dose among smokers with COPD. Smokers with COPD (n=45) stratified by EC use history (naïve vs. current use) will be randomized (1:1:1) to receive brief advice to switch to ECs, single session EC training, or enhanced EC training. Participants will complete an in-lab assessment of pre-intervention EC puff patterns followed by intervention and a follow-up assessment of resultant changes in EC puff patterns. Visits will be separated by a standard minimum 24-hour washout period. Participants will complete a final assessment of EC puff patterns at Wk 12. Immediately following completion of the second human lab visit, participants will receive 12 weeks of EC and assistance with switching, based on treatment allocation. Participants will complete in-person follow-up assessments throughout the 12-week switch period and those in the enhanced training arm will receive ongoing training.

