### **RANDOMIZED TRIAL OF EC TRAINING**

#### **RCT Assessments (see Table 1 for timing):**

**Cigarette smoking.** Cigarette smoking will be assessed at W0, W4, W8, and W12 using the Timeline Followback (TLFB) in which individuals report on number of cigarettes per day (CPD) in the past 7 days.

**eCO** levels will be used to biochemically confirm smoking status. eCO  $<6$  ppm will indicate a complete switch.

**Respiratory health and lung function.** The COPD assessment test (CAT) is a COPD-specific 8-item questionnaire designed to assess impairment in health status of COPD patients. Participants will complete the CAT at baseline and Wks 4, 8, and 12 to assess changes in self-reported respiratory health. Lung function will be assessed via spirometry.

Measure	Table 1. Measures by timepoint					
	SCRN	V1	Human Lab	W4	W8	RCT
Topography*		X	X	X	X	X
Nicotine boost		X	X			X
eCO	X	X	X	X	X	
7-day TLFB	X	X	X	X	X	X
Health effects						
Spirometry		X				X
COPD Gold Staging	X					X
CAT	X			X	X	X
Pulse wave velocity		X				X
Beat to beat blood pressure		X				X
6MWD		X				X
Other self-report						
Cigarette craving/withdrawal		X	X			X
mCES				X		X
Subjective effects of EC		X	X			X
Behavioral intentions	X			X		X

*Notes.* Topography measured throughout 12-week switching period

**6-minute walk distance** (6MWD) will assess changes in functional activity. The 6MWD assesses an individual's overall ability to conduct everyday activities and will be conducted at baseline, W4 and W12. This measure is particularly responsive to change in smokers with COPD. Specifically, improvements in 6MWD have been found within xx weeks of smoking reduction in smokers with COPD [ref].

**Changes in cardiovascular functioning** will be measured using Pulse Wave Velocity, a sensitive measure of arterial stiffness that shows rapid (~1 month) changes with switching to ECs, at baseline and W12. In addition, we will assess changes in beat-to-beat blood pressure from baseline to W12. Beat-to-beat blood pressure is a sensitive measure of blood pressure and vascular elasticity. Measures of cardiovascular functioning will be conducted by [name] and her team. These measures are sensitive to changes in smoking and vaping status and are associated with downstream health outcomes that result from smoking, such as cardiovascular disease.

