- e. **Between Week 0 and Week 4:** Participants will be provided with the device of their choice and pre-filled pods to use between visits for the real-world switch period. If chosen, the Evolv Reflex EC device will collect and store 4 weeks of data on the participant's EC use patterns and puffing topography. The JUUL and Vuse devices do not collect data. Research staff will conduct a brief phone check in with all participants on their switch date. During this call, a trained research assistant will assess tobacco and nicotine use since the last visit and will briefly trouble shoot barriers to switching to the e-cigarette.
- f. **RCT Visit – Week 4:** At Week 4 topography data will be downloaded from the EC and reviewed. In addition, participants will return their used and unused pods which will be weighed to assess e-liquid consumption between visits. Those in the Brief Advice and Single Session Training arms will not receive additional training. For those in the Enhanced Training arm, they will receive additional real-time feedback on their puff patterns. This arm is intended to mimic the level of support provided to smokers making a quit attempt using traditional quit smoking strategies and to determine the minimum level of support necessary to achieve a pattern of predominant EC use. Our approach with this arm is intentionally flexible to match the needs of each participant over the course of behavior change. For the purposes of rapport-building and continuity of care, attempts will be made to have participants meet with the same staff member each session. For participants in all study arms, the following will be done. Topography will be used to objectively and passively measure EC puff patterns. Participants will again complete eCO measurement to confirm smoking status. Cigarette smoking will be assessed using the TLFB in which individuals report on number of CPD in the past 7 days. To

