**G. Location where study will be performed:** All study visits will be completed at the Clinical Research Unit – Rainbow. During study visits where cardiovascular functioning is measured, participants will also visit [name] laboratory (KUMC campus; [name]). All data will be directly entered into an electronic data capture system (i.e., RedCap or CRIS), therefore minimizing the use of paper records. If paper records are generated, they will be stored in locked file cabinets. Only study staff will have access to the locked records and the secure online electronic data capture system.

**H. Collaboration (with another institution, if applicable):** N/A

**I. Single IRB Review for a Multi-site study (if applicable):** N/A

**J. Community-Based Participatory Research (if applicable):** N/A

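### The protocol rules out blinding for everyone, although the cardiovascular measures are run by a named team in its own laboratory that appears not to need to know the arm

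*Protocol*

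**What the plan says.** **Blinding.** Section II.C item 2: "This is an open-label trial. There is no blinding involved". Section II.B agrees: "The proposed study is an open label randomized clinical trial of EC training and training dose among smokers with COPD". No other section provides for masked assessors of any outcome.

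**Cardiovascular measures.** Section II.E.1 describes pulse wave velocity and beat-to-beat blood pressure, taken at baseline and Week 12, and adds: "Measures of cardiovascular functioning will be conducted by" a person (name removed) and that person's team. Section II.G places the study visits at the Clinical Research Unit and then says: "During study visits where cardiovascular functioning is measured, participants will also visit" a laboratory whose name is also removed.

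**Staff continuity.** Section II.E.2.f (Week 4 visit) says, while describing the Enhanced Training arm: "For the purposes of rapport-building and continuity of care", "attempts will be made to have participants meet with the same staff member each session". The text on procedures common to all arms starts after that, with "For participants in all study arms, the following will be done".

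**Role of the outcomes.** H2b in Section I.A predicts the largest health improvement with enhanced training, then single-session training, then brief advice. Section V.A estimates the differences in change between arms and describes the study as a pilot for effect sizes. Section V.B names change in puff duration as the primary endpoint.

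**The concern.** In a behavioural trial, open label is unavoidable for those who receive and those who deliver the training. It does not follow that the people who measure outcomes must know the arm. The protocol extends the statement to everyone and gives no reason.

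A tester who knows both the arm and the predicted ordering can influence a result without intending to. Even with an instrument-based measure there is judgement over which recordings to accept and which to repeat. Any such influence would tend to favour H2b, and a larger sample would not remove it. Because the pilot is meant to inform the design of the next trial, a biased arm difference would carry over into that planning.

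**Working it through.** No arithmetic applies. The protocol gives no figure on assessor bias, so the check is to set the sections side by side.

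1. **Does any section exempt assessors from the open-label statement?** No. Section II.C item 2 is categorical and Section II.B does not qualify it. Since the protocol fixes the matter in so many words, it has not been left to an analysis plan.

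2. **Is there a group of assessors who could be masked?** For the cardiovascular measures, apparently yes. Section II.E.1 names a team and Section II.G gives it a laboratory that participants visit in addition to the Clinical Research Unit. The training described in Section II.E.2.c and f is given by research staff at the study visits. Nothing gives the cardiovascular team a part in it or a reason to know the arm. As the names are removed, that this team is distinct from the trainers is an inference, though a natural one.

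3. **Would an ID-only request be enough?** Not alone. Section II.C item 1 ties the assignment to the sequential study ID, so anyone holding both the ID and the allocation list knows the arm. The list must be withheld too.

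4. **Which outcomes are reached?**
   - *Puff duration (primary, Section V.B):* recorded by a pressure sensor and the software in the device (Section II.E.2.c). Not reached.
   - *Pulse wave velocity and beat-to-beat blood pressure (Aim 2, H2b):* assigned to the cardiovascular team. Reached, and masking looks feasible.
   - *6MWD and spirometry (Aim 2, H2b):* these depend on effort, but no section says who runs them. Exposure is possible and is not established.
   - *Blood nicotine:* Section II.E item 5 lists what the sample label carries, and arm is not on it. Sections IV.B and IV.C call for labelling by study number. Largely covered already.

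5. **What does the continuity sentence add?** It describes an attempt, made for rapport, in the Enhanced-arm text. It does not say whether it covers training contacts only or measurement as well. The protocol therefore permits a trainer to test the same participant, without saying that this will happen.

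**The case against.** The other side has a good case. The protocol accurately calls itself an open-label behavioural pilot and claims no masking that it lacks. Pulse wave velocity and beat-to-beat blood pressure are instrument recordings, so the scope for tester influence is narrower than for a walk test or spirometry. Those more vulnerable tests are not assigned to the cardiovascular team, so masking that team does nothing for them. Participants know how much training they had. Their own effort may respond to that, and they may mention it to a tester. The primary comparison is untouched.

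All of this stands, and it limits the point to secondary health outcomes and a modest gain. It does not explain why a team that seems to have no need for the arm should be told it, or why the protocol should rule out masking that team.

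Three stronger readings are tempting, and the text does not support them:

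- *That the participant's coach will run the outcome tests.* Section II.E.2.f speaks only of attempts, within the Enhanced-arm text, and no section assigns the 6MWD, spirometry or TLFB to the coach.
- *That masking is free.* The protocol says nothing about its cost or about rostering.
- *That blood sample labels need a new rule.* Arm is not among the label contents already listed.

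**Conclusion.** The point holds in limited form. The protocol excludes all blinding and does not consider masked assessors, although the cardiovascular measures go to a named team in its own laboratory with no stated role in training. The consequence is an avoidable source of bias in Aim 2 health outcomes under H2b. The primary endpoint is not affected.

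The size cannot be derived from the protocol. A reader might assume that knowing the arm shifts a test by 0.1 to 0.3 SD and compare that with the 95% margin for a difference between two arms of 15, which is 1.96 × √(2/15) = 0.716 SD. The shift would then be 0.1/0.716 = 14% to 0.3/0.716 = 42% of the margin. That range has no source in the protocol, and it was framed for effort-dependent tests that are not assigned to the cardiovascular team. It should not be quoted as the size of this problem.

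The conclusion rests on two assumptions: that the cardiovascular team is distinct from the trainers, and that it does not need the arm for its work. The sponsor can confirm both.

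**What to change.** Replace Section II.C item 2 with wording such as:

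> *Participants and interventionists are not blinded. The cardiovascular laboratory team is not told the arm and has no access to the allocation list; requests carry the study ID only.*

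In Section II.E.2.f, state that the attempted same-staff continuity applies to training contacts. Add that, where existing staffing allows, a team member who did not train the participant runs the 6MWD, spirometry and Week 12 TLFB. Ask participants not to discuss their training with testers.

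This is a change of protocol wording plus an instruction to staff. It alters no treatment, endpoint or sample size. The downside is some rostering effort for the tests outside the cardiovascular laboratory, and occasional unmasking by participants.

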## **V. Data Analysis and Reporting**

**A. Statistical and Data Analysis:** The purpose of this pilot is to build a body of preliminary evidence and determine effect sizes for a fully powered R01 trial. To assess Aim 1, we will obtain means and SD for each variable at V1 and V2 and calculate mean change and SD of the change. Given that there is no difference at this stage in single and enhanced training arms, data for these arms will be combined. We will then construct 95% CIs on the change of each of these variables for treated and control groups. Obtain CI on the difference in the change between the two groups on each of these variables which will allow us to determine the short-term impact of training on outcome variables. To assess Aim 2, we will be able to estimate the proportion of subjects that fall into each of the switch patterns across the three treatment groups. Specifically, we will construct CIs on the proportion of predominant EC users. This would give us the data to determine effect sizes for the fully powered R01 trial. We will obtain means and SDs for each variable (i.e., health effects, puff patterns) at Wk0 and Wk12 and calculate mean change and SD of the change. We will then construct 95% CIs on the change of each of these variables for the three arms. We will obtain CI on the difference in the change between the three groups on each of these variables which will allow us to determine the longer-term impact of training on the outcome variables. Given the pilot nature of the study, we have limited ability to assess variables that may affect our

endpoints of interest, but initial correlations and associations will be examined to see if any of the variables (e.g., stratification variables including EC use history, gender) are related to our endpoints of interest.

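### The planned 95% CI margins for mean change in puff duration (0.76 s and 0.54 s) treat the SD as known; with the SD estimated, as planned, they are 0.83 s and 0.56 s at the same n

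*Protocol*

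**What the plan says.** Protocol section II.C.3 takes its variability from preliminary data: "the standard of change in puff duration over two weeks was 1.5 seconds per puff". The word after 'standard' is missing. It can only sensibly be read as a standard deviation, because the next sentence begins "Assuming a common standard deviation across groups" and because 1.5 used as an SD reproduces both margins.

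From this the section derives two precision statements for the acute phase (Human Lab Visits 1 and 2):

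- Brief advice: "15 participants will allow us to obtain a 95% CI with a margin of error of 0.76 for the mean change for brief advice".
- Single-session and enhanced training combined: "30 participants will allow us to obtain a 95% CI with a margin of error of 0.54 for the mean change in puff duration".

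On numbers, it says "Due to potential attrition, we will recruit up to 22 participants per group", and then "We will discontinue recruitment when we have 15 complete cases per group".

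For the Aim 1 analysis, section V.A says the trial will "calculate mean change and SD of the change" and then build 95% confidence intervals for the treated and control groups. It names neither the normal nor the t quantile. Section V.B makes change in puff duration the primary endpoint.

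**The concern.** The two margins are computed as if the SD were known, while the planned analysis estimates it from 15 or 30 people. A 95% interval for a mean with an estimated SD uses a t quantile, which at these sizes is visibly larger than 1.96. The printed margins are then smaller than the planned analysis would be expected to give at the assumed SD.

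This matters because section II.C.3 contains no power calculation. Interval width is the only reason given for 15 per arm, and two of its three precision figures concern the primary endpoint. The pilot's stated purpose is to supply effect sizes for a larger trial, so an accurate statement of how precisely they will be known is part of what it offers.

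**Working it through.** **Inputs (Protocol II.C.3).** SD of change 1.5 s; n = 15 (brief advice) and n = 30 (training arms combined); two-sided 95% intervals. The source of the SD in the analysis is the trial data (V.A).

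**Step 1. Reproduce the stated margins.** Half-width = z × SD/√n, with z = 1.96:

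- n = 15: 1.96 × 1.5/√15 = 0.759, stated as 0.76.
- n = 30: 1.96 × 1.5/√30 = 0.537, stated as 0.54.

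Both match. The other formulas tried do not: a one-sided normal quantile gives 0.637 and 0.450, and the estimated-SD versions below give larger values.

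**Step 2. Estimated SD, each group on its own.** Half-width = t(n−1) × SD/√n:

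- n = 15: 2.145 × 1.5/√15 = 0.831.
- n = 30: 2.045 × 1.5/√30 = 0.560.

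Ratios to step 1: 0.831/0.759 = 1.09 and 0.560/0.537 = 1.04. Against the printed figures the gaps are 0.83 − 0.76 = 0.07 s and 0.56 − 0.54 = 0.02 s.

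**Step 3. Estimated SD, pooled over the two groups.** This is the most favourable reading of the common-SD assumption, with 15 + 30 − 2 = 43 df:

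- n = 15: t(43) × 1.5/√15 = 0.781.
- n = 30: t(43) × 1.5/√30 = 0.552.

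Both are about 3% above step 1 and still above the printed values.

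**Step 4. What this means at a true SD of 1.5 s.**

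| | n = 15 | n = 30 |
|---|---|---|
| Printed margin | 0.76 | 0.54 |
| t margin, own SD | 0.83 | 0.56 |
| t margin, pooled SD | 0.78 | 0.55 |
| Average t half-width, own SD | 0.816 | 0.555 |
| Chance that the t half-width is within the printed margin | 37% | 43% |
| Same chance for a correctly stated t margin | 55% | 53% |
| Smallest n whose t margin meets the printed figure | 18 | 33 |

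The fifth row must be read against the sixth. Sample SDs vary, so even a correctly stated margin is met only a little over half the time. For the second group, 32 people are enough if rounding to 0.54 is allowed.

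**Step 5. Coverage, conditional on an analysis choice.** If 1.96 were also used with the estimated SD, coverage would be 93.0% (n = 15) and 94.0% (n = 30). This is a what-if; the protocol does not state that choice.

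**The case against.** **The sums are not wrong.** The normal quantile with an assumed SD is a common planning approximation, and both figures are correct under it. This stands. The point is optimistic precision, not a calculation slip.

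**The reported intervals need not undercover.** A reader might infer from the printed margins that the trial's intervals will be 93% or 94% intervals labelled 95%. The protocol does not support that. Section V.A says only that 95% intervals will be constructed, and the choice of quantile may properly be made in a statistical analysis plan, which was not available for this review. The coverage figures in step 5 remain conditional.

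**The stated precision might still be reached.** A reader might also conclude that 0.76 s and 0.54 s cannot be achieved. That goes too far. A single trial can have a low sample SD. The analysed number may also exceed 15 and 30: up to 22 per group may be recruited, Visit 2 follows Visit 1 by 1 to 5 days, and people lost between then and Week 12 would already have both acute measurements. With 18 and 33 analysed, the t margins would be 0.746 and 0.532. The protocol does not define a complete case or say whether later dropouts enter Aim 1, so this is possible but not planned. The printed margins are explicitly for 15 and 30.

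**Pooling shrinks the gap.** True, to about 3%, but it does not close it.

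**Nothing is decided by the difference.** No target precision is set and no test is powered on these margins. Uncertainty in the preliminary SD matters at least as much: if the SD were 1.65 s (an assumption, 10% higher), the normal margin at n = 15 would be 1.96 × 1.65/√15 = 0.84. This stands and limits the severity, but it is no reason to leave the printed figures as they are.

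**Conclusion.** The point holds and is minor. The margins in II.C.3 are obtained with the SD treated as known, and the planned analysis estimates it. At SD 1.5 s, with 15 and 30 people analysed, the matching t-based margins are 0.83 s and 0.56 s; with a pooled SD they are 0.78 s and 0.55 s. Neither version returns the printed values. Most of the weight lies with the 15-person brief advice arm; the difference between 0.54 and 0.56 is very small.

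The conclusion assumes that 1.5 s is the SD of change and that the analysed numbers are those stated. It does not show that the sample size is inadequate or that the analysis will be invalid.

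**What to change.** In Protocol II.C.3, replace 0.76 with 0.83 s and 0.54 with 0.56 s, and add that these are t-based margins at an SD of 1.5 s with 15 and 30 participants analysed. If the analysts intend to pool the SD over the two groups, print 0.78 s and 0.55 s and say so. Supply the missing word after 'standard' in the same edit.

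Keep the sample size. The change touches two numbers and a phrase and has no effect on design or conduct. Its only cost is a slightly less favourable statement of precision.

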using the Tiffany-Drobes Questionnaire on Smoking Urges – brief (QSU-brief) and Minnesota Nicotine Withdrawal Scale (MNWS) pre- and post-session. The mCES will assess subjective effects and sensory experiences at the end of each session. Participant's intentions for future use (e.g., purchase, use) of ECs will be assessed using a 4-item measure. At the end of the baseline vaping session, participants will be randomized and enrolled (stratified on EC history) to one of three study arms in a 1:1:1 fashion: 1) Brief Advice, 2) Single Episode Training, 3) Enhanced EC Training. See the Training Guild for Researcher for specific training. For the Brief Advice study arm, participants will be given brief advice to switch to the EC and basic instructions on use of the EC and refilling pods. Participants will view their topography post-intervention via the Escribe software while they puff. Based on our preliminary data, trained research staff will give feedback on puff parameters shown to differ between complete switchers and switch "failures" – puff duration, flow rate, inter-puff interval, and puff number. The session will last ~30 minutes. For the Enhanced EC training study arm, participants will receive the same training as the Single Episode Training arm. Participants will be asked to set a switch date using the Action Planning form. Participants will take the EC device home and use it as much or as little as they would like before the next visit. Lung function will be assessed via spirometry. At the end of the visit, a 6-minute walk distance (6MWD) test will be done to assess the participant's overall ability to conduct everyday activities. Baseline cardiovascular functioning will be measured using Pulse Wave Velocity, a sensitive measure of arterial stiffness that shows rapid (~1 month) changes with switching to ECs. Baseline beat-to-beat blood pressure will be measured to assess blood pressure and vascular elasticity. Participants will be compensated \$50 for this visit.

- d. **Human Lab Visit 2 / RCT Visit – Week 0 (1-5 days after Human Lab Visit 1):** Human Lab Visit 2 will occur 1-5 days after Human Lab Visit 2. Human Lab Visit 2 will be identical to Visit 1 but will not include any training, 6MWD test, or cardiovascular assessment. The purpose of this visit is to assess changes in topography following training at visit 1. Participants will be compensated \$50 for this visit.

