5. Samples will be labeled with a unique participant and study identification numbers, participant initials, visit date, and timepoint (-5, +30) and only members of [name] and [name]'s teams will have access to the samples. Samples will be disposed of one month after the final report is sent out to the Principal Investigator.
6. Timeline: We anticipate that this study will last 1 year (12 months; See Table 2 for timeline). We expect to recruit 5 participants in the third month of Q1 and 18 participants in each Q2 and Q3 and 4 participants in the final quarter. This accrual rate is commensurate with our past studies.

Table 2. Study timeline by quarter

Quarters (3 months)	Q1	Q2	Q3	Q4	Post-award
Staff training, REDCap, IRB	X				
Participant recruitment (N = 45)	5	18	18	4	
Human Lab Visits	X	X	X	X	
RCT	X	X	X	X	
Processing/sample analysis				X	
Data analysis				X	X
R01 preparation			X	X	X
Dissemination			X	X	

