### **III. Subject Participation**

#### **A. Recruitment:**

1. Our team has a record of successful recruitment of smokers that spans three decades. Our team has completed 7 large-scale, NIH-funded trials and recruited over 3,000 smokers in the past decade. Moreover, according to TUKHS patient database, there are over 3,700 smokers with COPD within Family Medicine alone. Based on this history and the available patient population, our enrollment goal of 45 smokers and e-cigarette users is comfortably feasible. Participants will be recruited through clinic (KUMC Department of Family Medicine), community-based efforts (e.g., flyers, face-to-face), and social media platforms including Facebook, Instagram, and Craigslist. Flyers will be placed around KUMC/TUKHS for patients to take. We will use the KUMC HERON and KUMC KUCC C3OD databases and the TMC/O2 electronic medical records to identify smokers. We will then send letters to patients on behalf of physicians (with prior physician approval) informing them of the study. In the letter, participants will be given the option to opt out of future study contact. Potential participants that do not opt out will be contacted by phone to assess interest in study enrollment/eligibility. We will also use the Frontiers registry to identify adult smokers who have agreed to be contacted for research. We will also use radio ads, word of mouth, and our existing pool of participants from prior studies. We will post the study to the KUMC Intranet list of current studies for KUMC employees. Additionally, participants are currently being screened for other research studies conducted by our team. Those who have completed studies or who are ineligible for other studies being conducted will be informed about the current study and offered the opportunity to be screened.
2. Recruitment methods are described above. Recruitment will be conducted by members of the study team. Recruitment will be overseen by [name]. Initial screening will be conducted over the phone and by redcap survey.
3. Advertisements and flyers that will be used for recruitment are attached. Advertisements and flyers will be handed out to potential participants by the study team and will be placed in clinics at KUMC/TUKHS.

4. Letters sent on behalf of physicians will be mailed directly to patients to inform them of the study. Within one week of mailing letters, study staff will make follow-up calls to patients who did not opt out and offer initial screening.

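### The protocol gives 45 both as the number randomised and as the number of complete cases, although its own attrition allowance permits up to 66 to be randomised

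*Protocol*

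**What the plan says.** Four places in the protocol treat 45 as the number of people entered.

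- II.B (Study Type and Design): "Smokers with COPD (n=45) stratified by EC use history", followed by 1:1:1 randomisation.
- II.C.1: "45 eligible smokers with COPD will be stratified by EC use history", again followed by 1:1:1 randomisation.
- II.E.6 (Timeline) and Table 2: "We expect to recruit 5 participants in the third month of Q1 and 18 participants in each Q2 and Q3", with 4 more in the last quarter. Table 2 labels the row with a recruitment total of 45. The same item says "We anticipate that this study will last 1 year".
- III.A.1 (Recruitment): "our enrollment goal of 45 smokers and e-cigarette users is comfortably feasible".

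II.C.3 uses the number differently. It asks for 15 complete cases in each group, expects attrition, and continues: "we will recruit up to 22 participants per group. We will discontinue recruitment when we have 15 complete cases per group".

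II.E.2.c fixes when a group comes into being. At the end of the baseline vaping session at Human Lab Visit 1, "participants will be randomized and enrolled (stratified on EC history) to one of three study arms".

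**The concern.** With 15 complete cases in each of three groups, 45 is a count of people who finish. In II.B, II.C.1, Table 2 and III.A the same 45 is a count of people who start. The two counts are equal only with no attrition, and II.C.3 says that attrition is expected.

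The extra places in II.C.3 cannot be read as a screening allowance. Someone lost before randomisation has no group, so a cap stated per group must count randomised participants.

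The maximum number of people exposed to study procedures, the accrual plan and the 12-month duration all depend on which number governs. So does the Week 12 precision in II.C.3, which is calculated for 15 participants per group.

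**Working it through.** **Inputs.** From II.C.3: 15 complete cases per group, a cap of 22 per group, an SD of change in puff duration of 1.5 s (the text omits the word deviation), stated margins of 0.76 s (n = 15) and 0.54 s (n = 30), and a Week 12 proportion margin of at most 0.25. From II.E.6 and Table 2: accrual of 5, 18, 18 and 4. The protocol states no attrition rate, so the 10%, 20% and 30% used below are assumptions.

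**1. The protocol's own margins.** With the normal quantile 1.96:
- Brief advice: 1.96 × 1.5/√15 = 0.759, stated as 0.76.
- Combined training: 1.96 × 1.5/√30 = 0.537, stated as 0.54.
- Proportion at p = 0.5: 1.96 × 0.5/√15 = 0.253, stated as at most 0.25.

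All three reproduce apart from rounding.

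**2. The two totals.**
- Table 2: 5 + 18 + 18 + 4 = 45.
- II.C.3 complete cases: 3 × 15 = 45.
- II.C.3 cap: 3 × 22 = 66, which is 21 more than 45.
- Attrition that the cap can absorb: 1 − 15/22 = 0.318, about 32%.

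**3. If II.C.3 governs.** Number to randomise for 15 completers per arm:
- 10%: 15/0.9 = 16.7, so 17 per arm and 51 in all.
- 20%: 15/0.8 = 18.75, so 19 per arm and 57 in all.
- 30%: 15/0.7 = 21.4, so 22 per arm and 66 in all.

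Table 2 shows accrual for none of these.

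**4. If 45 were the randomised total.** With 15 randomised per arm, expected completers and worst-case proportion margin (0.98/√n):
- 10%: 13.5 completers, 0.98/√13.5 = 0.27.
- 20%: 12 completers, 0.98/√12 = 0.28.
- 30%: 10.5 completers, 0.98/√10.5 = 0.30.

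The like-for-like starting value is 0.253.

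**5. Effect on accrual.** Q4 plans 4 recruits, against 18 in each of Q2 and Q3. At 18 per quarter it has room for 18 − 4 = 14 more.
- 51 needs 6 more, which fits.
- 57 needs 12 more, which fits.
- 66 needs 21 more, which exceeds the room by 7, or 7/18 ≈ 0.4 of a quarter.

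In addition, whether a participant completes is known only about 12 weeks after entry, so a recruitment stop based on completers lags behind accrual.

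**6. Side calculation: the primary between-group difference.** At 15 versus 30 and SD 1.5 s, the half-width is 1.96 × 1.5 × √(1/15 + 1/30) = 0.93 s, or 0.96 s with a pooled t on 43 degrees of freedom. II.C.3 does not give this figure.

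**The case against.** The best defence is that II.C.3 is explicit. It gives the requirement, the cap and the rule for ending recruitment, and it is the only place that deals with attrition. The 45 elsewhere could then be shorthand for the complete-case target. This stands as a guide to what was probably intended. It does not remove the contradiction, because II.B and II.C.1 say those 45 are randomised, and the timeline both says recruited and spreads exactly 45 over the quarters.

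The defence does limit the harm, and four stronger readings should not be drawn.

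- A reader might infer that the trial will end with about 10 completers per arm (15 × 15/22 = 10.2) and a Week 12 margin of about 0.31. That needs 45 to cap randomisation and the 15-completer rule in II.C.3 to be ignored. Under that rule, 32% attrition still leaves 15 of 22.
- A reader might infer that the primary endpoint loses precision. It is the change from before to after training or advice (V.B), measured at Visits 1 and 2 (V.A), and Visit 2 follows 1 to 5 days after Visit 1 (II.E.2.d). Attrition over 12 weeks bears mainly on Aim 2.
- A reader might infer that 66 participants need 21/18 ≈ 1.2 extra quarters of accrual. That overlooks the spare room in Q4.
- A reader might infer that 0.76 s and 0.54 s are wrong or are offered as the precision of the primary comparison. Both are labelled as margins for the mean change in a single group, both reproduce, and V.A already plans an interval for the difference. An interval for a difference is naturally wider than either single-group interval at the same SD. Its absence from II.C.3 is not an error.

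**Conclusion.** The contradiction holds and is wrong as written: 45 cannot be both the number randomised and the number of complete cases in a plan that allows for attrition. The gap is up to 21 participants (45 against a ceiling of 66). The 66 is a maximum and not a target.

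On the more natural reading, with II.C.3 governing, the planned precision is safe up to about 32% attrition, and the faults lie in the stated N, the Table 2 accrual and possibly the 12-month duration. Only if 45 were enforced as the randomised total would precision suffer, and then moderately: the worst-case Week 12 margin would go from 0.253 to between 0.27 and 0.30 at the assumed attrition of 10% to 30%.

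This should be corrected because the trial relies on the number, but nothing in the design or the planned analysis is invalid.

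**What to change.** In II.B, II.C.1, Table 2 and III.A, state that 45 is the complete-case target (15 per group) and that up to 66 participants (22 per group) may be randomised to reach it. Revise the Table 2 accrual to match, and check the 12-month duration against it, allowing for the 12 weeks before completion is known.

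The cost is a larger stated maximum N and possibly a longer timeline. By the accrual arithmetic above, 51 or 57 fit within Q4 at 18 per quarter, and 66 overruns by about 0.4 of a quarter, before the 12-week lag. Up to 21 further participants would also have to be resourced. Design and analysis do not change.

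As an optional addition, II.C.3 could report the 95% half-width for the primary between-group difference: 0.93 s by the protocol's own method, or 0.96 s by pooled t, at 15 versus 30 and an SD of 1.5 s.
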